7.9.2.6. Glycemic variability (measure from CGM)	21
7.9.2.7. HbA1c.....	21
7.9.2.8. Sensor glucose values surrounding SmartGuard triggered insulin suspensions (Treatment arm only).....	21
7.9.2.9. Proportion of Suspend before low events that reached the pre-set Low Limit (Treatment arm)	21
7.9.3. Analysis of tertiary endpoints.....	22
7.9.3.1. Mean number of SMBG	22
7.9.3.2. Questionnaires' scores	22
Gold Questionnaire	22
Hypoglycemia Fear Survey (HFS)	22
7.9.3.3. Total insulin dose	24
7.9.3.4. HbA1c level and number of sensor hypoglycemia events per week by subgroups	24
7.9.3.5. Mean weight.....	24
7.10. Safety Evaluation.....	25
7.10.1. Number of severe hypoglycemic events	25
7.10.2. Number of severe hyperglycemic events	26
7.10.3. Number of diabetic ketoacidosis events	26
7.10.4. Number of Serious Adverse Events, Serious Adverse Device Effects and Device Deficiencies	26
7.11. Health Outcomes Analyses.....	27
7.12. Changes to Planned Analysis.....	27
8. Validation Requirements	28
9. References	28

1. Version History

Version	Summary of Changes	Author(s)/Title
1.0	
• New Document	[REDACTED] [REDACTED]
2.0	
• For secondary endpoints related to hypoglycemic regions using CGM values, the StAP now only uses '<' consistently• Adds explanation on how to handle dates collected at baseline with missing day and/or month• Adds descriptive analysis of A1c by type of insulin (group 1: Lispro (Humalog), group 2: Aspart (Novolog), group 3: Glulisine (Apidra) and group 4: Other). This was prespecified in CIP.• Clarifies how the descriptive analysis of the PLGM will be performed• Per protocol criteria section is aligns with CIP recommended versus mandatory criteria.	[REDACTED] [REDACTED]

2. List of Abbreviations and Definition of Terms

Abbreviation	Definition
AE	Adverse Event
AUC	Area under the curve
CIP	Clinical Investigation Plan
CGM	Continuous Glucose Monitoring
CSII	Continuous Subcutaneous Insulin Infusion
DMC	Data Monitoring Committee
DTSQ	Diabetes Treatment Satisfaction Questionnaire
eCRF	electronic Case Report Forms
HFS	Hypoglycemia Fear Survey
ITT	Intent To Treat
LGS	Low Glucose Suspend
MAGE	Mean amplitude of glycemic excursions
MNSHE	Mean Number of Sensor Glucose Hypoglycemic Events
PP	Per Protocol
PLGM	Predictive Low Glucose Management
SAE	Severe Adverse Event
SAP	Sensor-Augmented Pump
SMBG	Self Monitoring Blood Glucose
StAP	Statistical Analysis Plan

3. Introduction

Managing type 1 diabetes requires constant vigilance and attention to diet, exercise, and insulin regimens, and depends on consistently delivering the right amount of insulin at the right time. Medtronic's insulin delivery systems have been helping type 1 diabetes subjects with their diabetes management for more than 30 years. The insulin pump system is indicated for the continuous delivery of insulin, at set and variable rates, for the management of diabetes mellitus in persons requiring insulin. Technological advances in insulin pump delivery systems and key clinical trials have established the value of this therapy in helping subjects with their daily diabetes management.

First improvement was real-time continuous glucose monitoring (CGM) data, used in conjunction with insulin pump therapy, allowing subjects to safely reduce their HbA1c values in comparison with multiple daily injection (MDI) therapy and continuous subcutaneous insulin infusion (CSII) alone by using CGM data to guide them in their insulin dosing regimen. Thereafter a feature was introduced, called Low Glucose Suspend (LGS), allowing the pump to automatically suspend insulin delivery when a pre-set sensor glucose threshold was reached. When this LGS feature is enabled in a Paradigm® Veo™ pump and a sensor glucose value at or below the pre-specified value is detected, the pump will stop insulin delivery for up to 2 hours, if not restarted earlier by the user. The benefits of sensor-augmented pump (SAP) therapy using this feature have been proven in several clinical trials, showing reduction in the incidence, severity and duration of hypoglycemic events. In addition, also data analyses based on routine real world use of pumps with the LGS feature confirm significant reductions in hypoglycemia.

The most recent advancement in SAP therapy is SmartGuard™. Medtronic's SmartGuard technology is implemented in the recently commercialized MiniMed™ 640G system and consists of the algorithms called, suspend on low, and suspend before low. The suspend on low is similar to the LGS algorithm in the Paradigm Veo pump and the Suspend before low feature, also called Predictive Low Glucose Management (PLGM), is the newest sensor algorithm that can suspend insulin delivery when the sensor glucose value is predicted to reach or fall below a pre-set low glucose limit within 30 minutes. In addition, the Suspend before low algorithm allows for automatic resumption of basal insulin delivery after 30-120 minutes, if the system predicts subject's recovery from hypoglycemia. During the suspension, insulin delivery can be manually resumed by the user at any time, and settings and alerts are customizable within multiple time blocks depending on the subject's needs in the MiniMed™640G system.

Hypoglycemia is an important barrier in achieving tight glycemic control. Even mild events of hypoglycemia have been shown to disrupt sleep, impair memory, and cause inflammatory reactions, with impacts on driving, work and daily living. Approximately one-third of subjects with type 1 diabetes have evidence of impaired hypoglycemia awareness, further increasing their risk of severe hypoglycemia. However, avoidance of hypoglycemia in these subjects has been shown to restore awareness in small-scale proof of concept studies. Until now, most studies of CSII and CGM therapy have excluded these subjects, and therefore, there are few studies to demonstrate if these technologies can provide an improvement specifically in this population.

The SMILE study will specifically recruit subjects with impaired awareness of hypoglycemia and aim to investigate if this technology can reduce the incidence of hypoglycemia in this group of high-risk subjects.

Despite the available clinical evidence, as described above, SAP therapy is not widely adopted, partly because CGM is not yet reimbursed in many countries. The current clinical evidence on the ability of SAP to reduce the risk of hypoglycemic events could be considered as not robust enough (e.g. short study duration, small number of subjects, not the right comparator, sub-optimal randomization process). Additional clinical evidence on the ability of SAP with SmartGuard technology to reduce the risk of hypoglycemic events can potentially lead to wider adoption and reimbursement of CGM technology to benefit subjects' needs.

This Statistical Analysis Plan (StAP) documents, before data is analyzed, the planning of final analyses that will minimally be included in study reports for the SMILE Study. This StAP is based on Version 1.0 (14 March 2016) of the SMILE Study Clinical Investigational Plan (CIP).

4. Study Objectives

Primary Objective: The primary study objective is to demonstrate a reduction in the mean number of hypoglycemic events when using the MiniMed 640G system with the SmartGuard algorithm:

The between arm difference in the incidence of hypoglycemic events below or equal to 55 mg/dL (3.0 mmol/L) during 6 months of SAP therapy (MiniMed 640G with SmartGuard), as compared to subjects on CSII therapy (MiniMed 604G) over the same period of time, in a population of T1 diabetic subjects with an increased risk of hypoglycemia, will be evaluated. A reduction in the mean number of hypoglycemic events below or equal to the threshold of 55 mg/dL (3.0 mmol/L) is estimated to be of clinical value. The evaluation will be made by comparing subject sensor data collected in both arms. The primary endpoint is the mean number of sensor glucose hypoglycemic events (MNSHE) per subject per week.

5. Investigation Plan

This is an international, multi-center, prospective, open-label, adaptive, randomized, controlled, pre-market clinical investigation with parallel arms. The study is designed to compare CGM-based hypoglycemic events in a treatment arm versus a control arm.

[figure not shown]
Enrolled subjects will enter a 2 weeks' run-in period, receive training and start CSII therapy with the MiniMed 640G insulin pump and usage of blinded Continuous Glucose Monitoring (CGM). At the end of the run-in period, eligible subjects that meet the randomization criteria will be randomized into the treatment phase of six (Figure 1) months in a 1:1 ratio to either:

- Treatment Arm: training and start of Sensor Augmented Pump therapy with Suspend before Low feature of SmartGuard turned ON.
- Control Arm: continuation of CSII therapy with blinded CGM usage for a total of 6 weeks during the treatment phase.

Sensor data is collected at 3 periods of 2 weeks. Period 1 starting at week 10 corresponds to 3 months after randomization, Period 2 starting at week 16 corresponds to 4.5 months after randomization and Period

3 starting at week 22 corresponds to 6 months after randomization. This study has an adaptive design. Due to the uncertainty about the hypoglycemic event rate and the magnitude of the true effect of treatment, the sample size will be re-estimated by an independent Data Monitoring Committee (DMC) in an interim assessment based on conditional power after a total of at least 60 subjects have been randomized and followed up for 6 months. Details of the interim analysis and adaptive design are available in the DMC Analysis Plan.

Figure 1: Study design overview

6. Determination of Sample Size

6.1. Statistical Hypothesis

There are 3 periods of 2 weeks in which sensor data is collected for both Treatment and Control arms. The mean number of sensor glucose hypoglycemic events (MNSHE) below or equal to 55 mg/dL (3.0 mmol/L) per subject/week will be calculated at each period using the sensor data collected in the TREATMENT arm (SAP with MiniMed 640G and SmartGuard) and the CONTROL arm (CSII with MiniMed 640G).

The overall MNSHE will be calculated as the average of P1, P2 and P3. The overall between group difference in MNSHE per week is of primary interest and will be compared using the following hypotheses:

Null-hypothesis: $H_0: \text{MNSHE}_{\text{TREATMENT}} = \text{MNSHE}_{\text{CONTROL}}$

Alternative hypothesis: $H_A: \text{MNSHE}_{\text{TREATMENT}} < \text{MNSHE}_{\text{CONTROL}}$

6.2. Sample size

The sample size calculation was performed based on assumptions from the results of the *ASPIRE study* (Bergenstal, et al., 2013). In particular, the mean number of sensor glucose hypoglycemic events below or equal to 55 mg/dL (3.0 mmol/L) per subject/week is expected to be 2 with standard deviation of 1.65 in the Control arm (CSII therapy alone with MiniMed 640G).

Assuming a two-sided two-sample t-test, alpha=0.05, power=80% and 40% reduction in the mean number of sensor glucose hypoglycemic events per subject/week in the Treatment arm (SAP with MiniMed 640G and SmartGuard), as compared to the control arm, the required sample size is 136 subjects (68 in each arm) completing the 6 month follow up of the study phase.

The dropout rate during the 6-month follow-up after randomization has been estimated to be around 15%. Incorporating this dropout rate, a total of 160 subjects will be randomized in a 1:1 ratio either to the SAP therapy arm (MiniMed 640G with SmartGuard) or to the CSII therapy arm (MiniMed 640G).

7. Statistical Methods

7.1. Study Subjects

7.1.1. Disposition of Subjects

Number of enrolled subjects and number of completed visits will be reported. An overview of study discontinuations will be provided. A description of the total numbers of subjects screened, randomized, per study arm, and a list of reasons for failed screening, dropouts number and corresponding reasons for dropping out will be reported.

A CONSORT flow diagram (Begg, Cho, & Eastwood, 1996), displaying the progress of all participants through the trial (Run-In phase: from Visit 1 to Visit 5 included, and Study phase: after Visit 5 to Visit 15 included) will report the number of subjects that contributed to primary objective analysis.

7.1.2. Per Protocol Criteria

Below there is a list of criteria that will be used to identify subject's data for the per protocol sensitivity analysis of the primary endpoint as described in section 7.1.3.2. Occurrence of each deviation will be

reported and occurrence of any deviation will result in exclusion of the subject from the per protocol analysis.

- Only for CONTROL arm subjects:
 - SmartGuard features should be turned OFF 100% of the time. To account for possible short time setting errors, a maximum of 1 day (0.55%) of the study period with SmartGuard features turned ON will be allowed, otherwise the subject's data will be excluded from PP analysis.
- Only for TREATMENT arm subjects:
 - Continuous unblinded sensor use is expected > 70% of the 6 months of the study phase, otherwise subject's data is excluded from the per protocol analysis.
 - While in sensor use, it is expected to have > 85% of time with Suspend before Low turned ON, otherwise subject's data is excluded from the per protocol analysis.
 - While in sensor use, exclude from Per Protocol if the low limit is outside the range (< 55mg/dL or >70mg/dL) for >50% of time.
- For both CONTROL and TREATMENT arms:
 - Pump usage/wear: In both arms, pump wear is expected to be a minimum of 80% of the 6 months study phase time. Exclude from PP analysis if pump wear is less than 80% of the time (this includes both, pump data loss and days with Total Daily Dose =0).
 - Average number of SMBG per day should be >2; otherwise exclude from PP analysis.
 - Sensor usage during the 3 periods of 2 weeks (starting at weeks 10, 16 and 22), for the assessment of the primary endpoint, will be monitored for each subject. Combining the three periods, a total of 6 weeks of sensor data is expected but a subject's data is excluded from PP analysis if a subject has less than 3 weeks of sensor data when the 3 periods are combined (this is equivalent to <50% of the time for P1+P2+P3). The total number of subjects with less than 3 weeks of sensor will be reported.
 - Exclude from PP analysis if a subject drops out of the study phase of 6 months. Number of subjects dropping out of the study phase will be reported
 - The length of follow-up, from visit 6 to visit 15, should be within a window of 161 days to 182 days (calculated from the date of visit 6, 168-7 days study phase duration or 168+14 days study phase duration). If the length of follow-up is less than 161 days, exclude from PP analysis.

7.1.3. Analysis Sets

7.1.3.1. Efficacy analysis set

For the primary endpoint, efficacy analyses will be performed in the Intent to Treat (ITT) basis. The ITT set will be composed of all randomized subjects. These subjects will be assessed and analyzed as members of the intended randomized arm, irrespective of their compliance to the planned course of treatment or deviations from protocol.

7.1.3.2. Per Protocol set

For sensitivity purposes, efficacy analysis of the primary endpoint will also be performed on the Per Protocol set. The Per Protocol (PP) set is defined as the set of successfully randomized subjects with no violation of entry criteria and who are compliant with the protocol. The PP set will include subjects who do not have any deviations as listed in section 7.1.2.

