7.5. Adjustments for Multiple Comparisons

The following hierarchical test procedure reflects the relative importance of the endpoints and controls for multiplicity.

- Primary study endpoint

The mean number of sensor glucose hypoglycemic events ≤ 55 mg/dL will be tested for superiority as described in section 7.9.1 and a p-value <0.05 will be considered statistically significant.

- Fixed sequential testing of selected secondary endpoints

For the following endpoints, the procedure test hierarchically the ordered hypotheses in sequence at level $\alpha=0.05$ until a first hypothesis is non-rejected.

1. Mean Time spend ≤ 55 mg/dL

Superiority test, if p-value ≤ 0.05 reject null hypothesis and continue, else stop

2. Mean Time in target 70-180mg/dL

Non-inferiority test with non-inferiority margin of 40 minutes, if p-value ≤ 0.05 reject null hypothesis and continue, else stop

3. Mean Time in target 70-180mg/dL

Superiority test, if p-value ≤ 0.05 reject null hypothesis.

- Exploratory analysis

For the endpoints listed below and for all other endpoints, hypothesis testing may be performed and p-values will be reported but may not be claimed

- The mean number of sensor glucose hypoglycemic events < 54 mg/dL

- Mean Time spend < 54 mg/dL

- HFS score (Superiority test, exploratory only)

- DTSQs and DTSQc (Superiority test, exploratory only)

- Mean Time spend > 180 mg/dL (Non-inferiority test with non-inferiority margin of 40 minutes, exploratory only)

- Mean duration of hypoglycemic excursions < 54 mg/dL (Superiority test, exploratory only)

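### The confirmatory non-inferiority test of time in range has no named analysis set and no per-protocol support, so non-use of the feature could hide part of a true loss

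*SAP*

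**What the plan says.** SAP 7.1.2 lists criteria for a "per protocol sensitivity analysis of the primary endpoint as described in section 7.1.3.2". SAP 7.1.3.2 carries the same limit: "efficacy analysis of the primary endpoint will also be performed on the Per Protocol set". For the treatment arm the criteria cover sensor use over the six months, the low-limit setting, and use of the feature: "While in sensor use, it is expected to have > 85% of time with Suspend before Low turned ON".

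SAP 7.1.3.1 is also confined to one endpoint: "For the primary endpoint, efficacy analyses will be performed in the Intent to Treat (ITT) basis". That set is all randomised subjects, analysed "irrespective of their compliance to the planned course of treatment or deviations from protocol".

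SAP 7.5, under "Fixed sequential testing of selected secondary endpoints", has three steps after the primary test: superiority on time at or below 55 mg/dL, then time in 70-180 mg/dL tested as "Non-inferiority test with non-inferiority margin of 40 minutes, if p-value ≤ 0.05 reject null hypothesis and continue, else stop", then superiority on the same endpoint. SAP 7.9.2.5 repeats the margin and expresses the endpoint per day, so the margin is 40 minutes per day. SAP 7.9.2 carries the primary model over to secondary endpoints but names no analysis set. SAP 7.4 adds no adherence-based analysis. Protocol H.1 describes only an intention-to-treat analysis, on a set that also requires at least two weeks of CGM.

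**The concern.** In a superiority test, subjects who do not use the treatment usually pull the estimate towards no difference, which works against the claim. A non-inferiority test guards against a true loss, and there the same pull can work for the claim. The plan therefore provides its per-protocol check where non-use is conservative and omits it from the one confirmatory test where non-use is not reliably so.

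Step 2 can be claimed, and it is the gate to step 3. A loss is not ruled out by the documents: protocol J.2.5 warns that SmartGuard may activate when glucose is not low. The SAP also foresees non-use, since it sets exclusion thresholds for it. A subject who wears the sensor with the feature off still supplies time-in-range data, as does a low-wear subject with at least three days of data in a period (SAP 7.7.2). As planned, a reader of a non-inferiority claim could not tell whether it also holds in subjects who used the feature.

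**Working it through.** **Inputs from the SAP.** Margin 40 min/day (7.5, 7.9.2.5). Primary design: control mean 2 events/week, SD 1.65, 40% reduction (difference 0.8), two-sided 0.05, power 80%, 68 per arm, 15% dropout, 160 randomised (6.2).

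**Inputs assumed.** The documents give no SD for time in range and no expected non-use. I take SD 100 to 200 min/day, and a fraction q of 10 to 30% of treatment subjects with no treatment effect at all. SAP 7.5 does not state the sidedness of its p-value threshold, so both one-sided 0.025 and 0.05 are shown.

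**1. The plan's own figure.** A two-sided t-test with difference 0.8 and SD 1.65 needs 67.75, so 68 per arm and 136 in total. 136/0.85 = 160. This reproduces the SAP. No size or power is stated for the non-inferiority test, so I use 68 per arm.

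**2. Dilution of a loss.** Observed loss = (1 − q) × true loss in users. The true loss that appears as exactly 40 is 40/(1 − q):
- q = 10%: 40/0.90 = 44.4 min/day
- q = 15%: 40/0.85 = 47.1
- q = 20%: 40/0.80 = 50.0
- q = 30%: 40/0.70 = 57.1

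**3. Chance of claiming non-inferiority when users truly lose 40 min/day.** P = Φ[(40 − (1 − q) × 40)/(SD × √(2/68)) − z]. For SD 100 and q = 20%: the standard error is 100 × √(2/68) = 17.15, 8/17.15 = 0.47, 0.47 − 1.96 = −1.49, so P = 6.8%.

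| q | Observed loss | One-sided 0.025: SD 100 / 150 / 200 | One-sided 0.05: SD 100 / 150 / 200 |
|---|---|---|---|
| 0% | 40 | 2.5 / 2.5 / 2.5% | 5.0 / 5.0 / 5.0% |
| 10% | 36 | 4.2 / 3.6 / 3.3% | 7.9 / 6.8 / 6.3% |
| 20% | 32 | 6.8 / 5.0 / 4.2% | 11.9 / 9.1 / 7.9% |
| 30% | 28 | 10.4 / 6.8 / 5.4% | 17.2 / 11.9 / 9.8% |

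These are error rates for a statement about users, conditional on reaching step 2. For the effect of assignment, the as-randomised test keeps its nominal level.

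**4. Direction when there is no loss.** With SD 150 and one-sided 0.025, a true difference of zero gives 34.3% at both q = 0 and q = 30%, so there is no change. A true gain of 30 min/day gives 77.7% at q = 0 and 66.0% at q = 30%, so the chance of the claim falls.

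**5. Effect of the same non-use on the gate.** Primary power = Φ[(1 − q) × 0.8/(1.65 × √(2/68)) − 1.96], with standard error 0.283:
- q = 0: 2.83 − 1.96 = 0.87, about 81% (80% by the t-test)
- q = 15%: 0.68/0.283 − 1.96 = 0.44, about 67%
- q = 30%: 0.56/0.283 − 1.96 = 0.02, about 51%

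**The case against.** A reader might infer that non-adherence always favours the non-inferiority claim. The documents do not support that. They state no expected loss, step 3 tests for a gain on the same endpoint, and with a zero effect or a gain dilution does not help the claim (working, step 4).

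A reader might also count controls who switch the feature on. They have little practical route: their transmitters are not linked to the pump (protocol B.3.1.1), they record blinded for only six weeks of the treatment phase (B.3), and run-in transmitters are collected at Visit 5 (F.3.5). The case rests on the treatment arm.

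Further objections have weight:
- Step 2 is reached only after superiority on the primary endpoint and on time at or below 55 mg/dL. Heavy non-use would weaken those tests too.
- No effect at all in non-users is a worst case. With the feature off they still see CGM values and alerts (protocol B.2.2), and a subject with the feature on for 84% of sensor time fails the criterion yet is well exposed. Run-in screening (D.3) and compliance review with retraining (F.3.9, F.3.11, F.3.13) should limit non-use.
- The per-protocol exclusions are made after randomisation and differ by arm: three usage criteria for treatment, one for control. They also drop subjects for dropout, short follow-up, few SMBG readings or low pump wear, none of which isolates feature use.
- The as-randomised effect fits the protocol's aim of efficacy in home settings (B.1).
- Each per-protocol deviation and treatment-arm sensor wear will be reported (SAP 7.1.2, 7.7.1).

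These points limit the size of the problem and argue against a rule that both sets must pass. They do not supply the missing analysis set or a pre-specified supporting analysis.

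**Conclusion.** The gap stands in a conditional form and is a cheap improvement. It does not affect the primary analysis. The per-protocol analysis covers only the primary superiority test, and the confirmatory time-in-range non-inferiority test has neither a named set nor a per-protocol repeat. Reading 7.9.2 together with 7.1.3.1 suggests all randomised subjects, but that is inference.

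If the device truly reduces time in range, non-use makes a 40-minute claim easier. Under an assumed complete absence of effect in non-users, a loss of 47 min/day in users appears as 40 at 15% non-use. With a true loss at the margin, the chance of a false claim about users rises from 2.5% to 4.2-6.8% at 20% non-use (assumed SD 100 to 200, 68 per arm, one-sided 0.025). Real dilution may well be smaller. The documents do not support reading these figures as expected errors, or concluding that the claim would succeed because subjects left the feature unused.

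**What to change.** In SAP 7.1.3.2 and 7.5 step 2, with a matching line in 7.9.2.5:
- State that the non-inferiority test is run on all randomised subjects as the main analysis, and that this result governs the sequence.
- Repeat it on the existing per-protocol set as a pre-specified supporting analysis.
- Report both confidence intervals against the 40-minute margin.
- If the per-protocol interval crosses the margin, report that non-inferiority is not confirmed in adherent subjects.

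The cost is one model run on a set already defined, and possibly a more qualified claim. The per-protocol result needs caution because of its post-randomisation, arm-specific exclusions and its smaller size. For example, with an assumed SD of 150, a gain of 30 min/day and 50 per arm, the standard error is 150 × √(2/50) = 30, and 70/30 − 1.96 = 0.37 gives about 65% power, against 78% with 68 per arm. For that reason it should support the main analysis and not decide the test.
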